## **8.6 Investigator's Site File**

At each study site, the investigator is responsible for maintaining all records to enable the conduct of the study to be fully documented. Essential documents as required by GCP guidelines and regulations (e.g., copies of the protocol, study approval letters, all original informed consent forms, site copies of all CRFs, drug dispensing and accountability logs, correspondence pertaining to the study, etc.) should be filed accurately and kept by the investigator for the maximum period of time required by local regulations.

The investigator is responsible for maintaining a confidential subject identification code list, which provides the unique link between named source records and CRF data for the Sponsor. The investigator must arrange for the retention of this confidential list for the maximum period of time required by local regulations.

No study document should be destroyed without prior written agreement between the investigator and the Sponsor. Should the investigator elect to assign the study documents to another party, or move them to another location, the Sponsor must be notified in writing.

## **8.7 Provision of Additional Information**

On request, the investigator will supply the Sponsor with additional data relating to the study, or copies of relevant source records, ensuring that the subject's confidentiality is maintained. This is particularly important when CRFs are illegible or when errors in data transcription are encountered. In case of particular issues or governmental queries, it is also necessary to have access to the complete study records, provided that the subject's confidentiality is protected in accordance with applicable regulations.

## **8.8 Independent Data Monitoring & Endpoint Adjudication Committee**

An Independent Data Monitoring & Endpoint Adjudication Committee (IDMEAC) will be established by the Sponsor. The IDMEAC will be composed of recognised experts in the field of clinical care who are not actively recruiting subjects.

The IDMEAC will review relevant data periodically during the study and will give advice on the continuation, modification, or termination of the study. This committee will also be responsible for adjudicating the primary and secondary efficacy endpoints in the study.

A IDMEAC charter will define in detail the composition, responsibilities and procedures of the IDMEAC.

## 9 STATISTICAL METHODS AND SAMPLE SIZE

The statistical analysis will be delegated under an agreement of transfer of responsibilities to an external Contract Research Organization (CRO). All Octapharma procedures and policies have to be met by this CRO. Discrepancies or exceptions are to be approved by the Sponsor's Manager of Biometrics.

A statistical analysis plan (SAP) describing all details of the analyses to be performed will be prepared by the study statistician and approved by the Sponsor before the start of the study.

Due to the low number of patients, all statistical analysis will be descriptive only.

Continuous variables will be summarised using descriptive statistics (including arithmetic mean, standard deviation (SD), median, minimum and maximum, number of observations and missing observations). Categorical variables will be summarised with counts and percentages.

### 9.1 Sample Size

The number of subjects is limited by the very small number of patients with this indication. At least 12 patients will undergo PK assessments in this study. The minimum number of paediatric patients with a haemostatic outcome assessment for the on-demand treatment of a bleeding episode will be 6 and has been agreed upon with the paediatric committee of the EMA. No confirmatory test is provided. Therefore, no sample size estimation is provided.

### 9.2 Populations for Analysis

#### 9.2.1 Safety Population

The safety population will include all subjects who received at least one infusion of the IMP. The analysis of safety will be based on this population.

#### 9.2.2 Full Analysis Set

The full analysis set (FAS) defined according to the intention-to-treat (ITT) principle will include subjects who fulfil all of the following conditions:

- Received at least one infusion of the IMP
- Entered the study with a confirmed congenital fibrinogen deficiency (second inclusion criterion; see Section 4.2)

### 9.2.3 PK Analysis Population

The PK analysis population includes all patients of the FAS who started the PK assessment and have at least one valid post-baseline fibrinogen activity level.

### 9.2.4 PK-PP Population

The PK-PP population includes patients in the PK analysis population who completed the PK sampling phase without significantly violating the inclusion/exclusion criteria or other aspects of the protocol considered to potentially affect the PK results:

Especially patients will be excluded from this population, if they meet the following protocol deviations:

- Bleeding disorder other than congenital fibrinogen deficiency, including dysfibrinogenae-mia
- Any fibrinogen concentrate or other fibrinogen-containing blood product within 2 weeks prior to start of treatment for the PK phase
- Diagnosis or suspicion of a neutralising anti-fibrinogen inhibitor currently or at any time in the past
- Patients who use concomitant medication before or during the PK phase that may confound study results
- Patients who receive less than 90% of the planned dose (nominal)
- Fibrinogen baseline measurement for PK assessment missing
- More than 2 post-baseline blood samples missing for PK assessment

### 9.2.5 FirstBLEED Population

The FirstBLEED population will include subjects of the FAS who fulfil the following condition:

- Presented with at least one episode of acute bleeding (third inclusion criterion; see Section 4.2) treated with *Octafibrin*

### 9.2.6 FirstBLEED-PP Population

The FirstBLEED-PP population will include subjects of the FirstBLEED population who fulfil the following conditions:

- Provide valid, i.e., non-missing, haemostatic efficacy data for their first bleeding
- Received  $\geq 90\%$  of the planned total dose of the IMP in the first infusion for their first bleeding
- Received  $\geq 80\%$  of the calculated dose (if no dose was calculated, 0% will be assumed) of the IMP over all further infusions of the first bleeding according to the treatment schedule

- Did not meet any of the following exclusion criteria:
  - Bleeding disorder other than congenital fibrinogen deficiency
  - End-stage liver disease (i.e., Child-Pugh-score B or C)
  - Suspicion of an anti-fibrinogen inhibitor as indicated by previous IVR, if available  $<0.5$  (mg/dL)/(mg/kg)
  - Treatment with any fibrinogen concentrate or other fibrinogen-containing blood product within 2 weeks prior to start of treatment for the bleeding episode
- Did not use any coagulation-active drug (i.e., non-steroidal anti-inflammatory drugs, warfarin, coumarin derivatives, platelet aggregation inhibitors) within 1 week prior to start of treatment for the first bleeding episode, or as a planned or expected medication during the time period from Day 1 until 24 hours (i.e., 1 day) after the last *Octafibrin* infusion

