#### Additional Octafibrin infusions, as required

- Additional infusions of *Octafibrin* **should** be administered if the actual fibrinogen plasma level measured on subsequent study days is below the accepted lower limit of the target level (80 mg/dL for minor bleeding, 130 mg/dL for major bleeding).
- If the actual fibrinogen plasma level is above the accepted lower limit of the target level, *Octafibrin* **should not** be administered.

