#### 1 hour ( $\pm 15$ minutes) after the end of infusion:

- Vital signs
- TEE questionnaire
- Blood draw for:
  - fibrinogen plasma level (local lab–activity; central lab–antigen and activity)
  - MCF
- AEs and concomitant medications

3 hours ( $\pm 15$  minutes) after the end of infusion:

- Vital signs
- TEE questionnaire
- Blood draw for:
  - fibrinogen plasma level (central lab—antigen and activity)
  - thrombogenicity
- AEs and concomitant medications

**NOTE:** If, in the investigator's judgement, the infusion of *Octafibrin* administered on Day 1 is deemed the only infusion needed for treatment of the subject's bleeding event, the subject will need to reach the end of the treatment observation period, where the "24 hours (i.e., 1 day) after the last infusion" assessments should be performed.

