#### **First infusion of Octafibrin**

Following the pre-operative assessments and within 3 hours before the start of surgery, the subject may receive the first infusion of *Octafibrin* (see Section 5.4).

**NOTE:** If, in the investigator's judgement, there are no additional infusions of *Octafibrin* needed to prevent bleedings post surgery, the post-infusion assessments as detailed in the schedule for the **Last Post-Operative Day** should be performed instead.

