## 6 STUDY POPULATIONS

### 6.1 Subject Disposition

For the analysis of this study, the following populations will be considered:

Safety Set: All subjects who received at least one infusion of *Octafibrin*. The analysis of safety will be based on this population.

Full Analysis Set: The full analysis set (FAS) defined according to the intention-to-treat (ITT) principle will include subjects who fulfil all of the following conditions:

- received at least one infusion of the IMP.
- entered the study with a confirmed congenital fibrinogen deficiency

Pharmacokinetic analysis set (PK): All patients of the FAS who started the PK assessment and have at least one valid post-baseline fibrinogen activity level.

Pharmacokinetic per protocol analysis set (PK-PP): All patients of the PK analysis set who completed the PK sampling phase without significantly violating the inclusion/exclusion criteria or other aspects of the protocol considered to potentially affect the PK results.

Especially patients will be excluded from this population, if they meet the following protocol deviations:

- Bleeding disorder other than congenital fibrinogen deficiency, including dysfibrinogenaemia
- Any fibrinogen concentrate or other fibrinogen-containing blood product within 2 weeks prior to start of treatment for the PK phase
- Diagnosis or suspicion of a neutralising anti-fibrinogen inhibitor currently or at any time in the past
- Patients who use concomitant medication before or during the PK phase that may confound study results
- Patients who receive less than 90% of the planned dose (nominal)
- Fibrinogen baseline measurement for PK assessment missing
- More than 2 post-baseline blood samples missing for PK assessment

First bleeding analysis set (firstBLEED): subjects of the FAS who have at least one episode of acute bleeding treated with *Octafibrin*.

First bleeding per protocol analysis set (BLEED-PP): All patients from the FirstBLEED analysis set who fulfil the following conditions:

- Provide valid, i.e., non-missing, haemostatic efficacy data for their first bleeding
- Received  $\geq 90\%$  of the planned total dose of the IMP in the first infusion for their first bleeding
- Received  $\geq 80\%$  of the calculated dose (if no dose was calculated, 0% will be assumed) of the IMP over all further infusions of the first bleeding according to the treatment schedule
- Did not meet any of the following exclusion criteria:

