  - Bleeding disorder other than congenital fibrinogen deficiency
  - End-stage liver disease (i.e., Child-Pugh-score B or C)
  - Suspicion of an anti-fibrinogen inhibitor as indicated by previous IVR, if available  $<0.5$  (mg/dL)/(mg/kg)

- Treatment with any fibrinogen concentrate or other fibrinogen-containing blood product within 2 weeks prior to start of treatment for the bleeding episode.
- Did not use any coagulation-active drug (i.e., non-steroidal anti-inflammatory drugs, warfarin, coumarin derivatives, platelet aggregation inhibitors) within 1 week prior to start of treatment for the first bleeding episode, or as a planned or expected medication during the time period from Day 1 until 24 hours (i.e., 1 day) after the last *Octafibrin* infusion

Bleeding analysis set (BLEED): all documented bleeding episodes treated with *Octafibrin* in subjects of the FAS.

Bleeding per protocol analysis set (BLEED-PP): all documented bleeding episodes with no major protocol deviations, i.e. fulfilling the following conditions:

- Fully documented haemostatic efficacy data available for the bleeding
- $\geq 90\%$  of the planned total dose of the IMP was given for the bleeding
- $\geq 80\%$  of the calculated dose (if no dose was calculated, 0% will be assumed) of the IMP was given over all further infusions of the bleeding according to the treatment schedule
- The patient with the respective bleeding did not meet any of the following exclusion criteria:
  - Bleeding disorder other than congenital fibrinogen deficiency
  - End-stage liver disease (i.e., Child-Pugh-score B or C)
  - Suspicion of an anti-fibrinogen inhibitor as indicated by previous IVR, if available  $<0.5 \text{ (mg/dL)/(mg/kg)}$
  - Treatment with any fibrinogen concentrate or other fibrinogen-containing blood product within 2 weeks prior to start of treatment for the bleeding episode.
- The patient with the respective bleeding did not use any coagulation-active drug (i.e., non-steroidal anti-inflammatory drugs, warfarin, coumarin derivatives, platelet aggregation inhibitors) within 1 week prior to start of treatment for the first bleeding episode, or as a planned or expected medication during the time period from Day 1 until 24 hours (i.e., 1 day) after the last *Octafibrin* infusion

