Surgery analysis set (SURG): all documented surgical interventions with a need for at least one infusion of the IMP during the time period from the day of surgery until day of overall clinical assessment of post-operative efficacy in subjects of the FAS.

Surgery per protocol analysis set (SURG-PP): all surgeries of the SURG analysis set, where the patients underwent the surgery fulfil the following conditions:

- Provide valid, i.e., non-missing, intra- and post-operative efficacy data for the surgery
- Received  $\geq 90\%$  of the planned total dose of the IMP in the first infusion prior to the surgery
- Received  $\geq 80\%$  of the calculated dose (if no dose was calculated, 0% will be assumed) of the IMP over all further infusions of the surgery according to the treatment schedule
- Did not meet any of the following exclusion criteria:
  - Bleeding disorder other than congenital fibrinogen deficiency
  - End-stage liver disease (i.e., Child-Pugh-score B or C)
  - Suspicion of an anti-fibrinogen inhibitor as indicated by previous IVR, if available  $<0.5 \text{ (mg/dL)/(mg/kg)}$
  - Treatment with any fibrinogen concentrate or other fibrinogen-containing blood product within 2 weeks prior to start of treatment for the bleeding episode.

- Did not use any coagulation-active drug (i.e., non-steroidal anti-inflammatory drugs, warfarin, coumarin derivatives, platelet aggregation inhibitors) within 1 week prior to start of treatment for the first bleeding episode, or as a planned or expected medication during the time period from Day 1 until 24 hours (i.e., 1 day) after the last *Octafibrin* infusion

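### Read literally, the per-protocol dose rule for further infusions excludes bleeds and surgeries treated with one infusion, though the protocol foresees such treatment; no exemption is stated

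*Protocol*

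**What the plan says.** Protocol 9.2.6 sets two dose conditions for FirstBLEED-PP. The first is at least 90% "of the planned total dose of the IMP in the first infusion for their first bleeding". The second is at least 80% "of the calculated dose (if no dose was calculated, 0% will be assumed) of the IMP over all further infusions of the first bleeding". Because the first infusion has its own condition, the second concerns later infusions only.

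SAP 6.1 carries the second condition, including "if no dose was calculated, 0% will be assumed", into three sets:
- the first-bleed per-protocol set (abbreviated BLEED-PP there, but called FirstBLEED-PP in SAP 7);
- the all-bleeds set, where the 80% threshold is worded as "of the calculated dose (if no dose was calculated, 0% will be assumed) of the IMP was given over all further infusions of the bleeding";
- SURG-PP, with at least 80% "of the calculated dose (if no dose was calculated, 0% will be assumed) of the IMP over all further infusions of the surgery".

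None of them exempts a case in which no further infusion was due.

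The protocol foresees treatment with one infusion. Protocol 6.1.3.1 has a note for the case where the Day 1 infusion "is deemed the only infusion needed for treatment of the subject's bleeding event". Protocol 6.1.4.1 has a matching note for surgery, where no more infusions are "needed to prevent bleedings post surgery". Protocol 6.1.3.2 and 6.1.4.2 tell the site not to give Octafibrin on a day when the level is at or above the accepted lower limit.

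Protocol 9.2.9 and SAP 7 name FirstBLEED as the primary population for the primary endpoint and FirstBLEED-PP as the secondary one. SAP 6.1 defines its age subpopulations on BLEED-PP and SURG-PP.

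**The concern.** A child treated as the protocol instructs, whose level stays at or above the limit after one infusion, can fail a criterion meant to identify protocol-compliant treatment. Protocol 9.2.8 and 9.2.9 describe the all-bleeds and surgery per-protocol sets as cases without major deviations, and a single infusion is not among the major deviations listed in SAP 6.2.

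Two programmers could build different sets from the same data. Set membership is settled around database lock in an open-label study, when outcomes may already be known. The note at the end of Protocol 9.2.9 requires written agreement only for exclusions beyond the listed ones; it gives no route for bringing back a case that a listed criterion removes. SAP 14 drops separate per-protocol output if nobody is excluded, so the choice of reading could even decide whether per-protocol tables are produced. With a minimum of two surgeries, SURG-PP could be empty.

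**Working it through.** The plan states no sample-size or power figure to reproduce. The check has four steps.

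**1. The rule under three readings.**

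| Reading | One infusion only | Further infusion given, no dose calculated |
|---|---|---|
| A. No calculated dose means 0% (literal) | 0% < 80%: out | 0% < 80%: out |
| B. Criterion does not apply if there was no further infusion | in | out |
| C. Calculated dose is taken as zero | 0 ≥ 0.8 × 0: in | in |

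A is the most direct reading. The three do not agree on either column.

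**2. Size of the per-protocol set.** Inputs: the minimum of 6 first bleeds (Protocol 9.1) and the two-sided 95% Clopper-Pearson interval (Protocol 9.3.1). Assume no other exclusions, all bleeds successful, and k single-infusion first bleeds. Under reading A, n = 6 − k. When all n succeed, the lower limit is 0.025^(1/n) and the upper limit is 100%.

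| k | n | Lower limit |
|---|---|---|
| 0 | 6 | 54.1% |
| 1 | 5 | 47.8% |
| 2 | 4 | 39.8% |
| 3 | 3 | 29.2% |
| 4 | 2 | 15.8% |
| 5 | 1 | 2.5% |
| 6 | 0 | set empty |

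Under a reading that keeps these cases, n = 6 and the limit is 54.1% whatever k is.

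**3. How often one infusion might suffice.** Inputs: targets 100 and 150 mg/dL with limits 80 and 130 mg/dL (Protocol 5.4.3); half-life 3 to 5 days in normal physiology (Protocol 1.1). Let E be the endogenous level, T the target and h the half-life. Then level(t) = E + (T − E) × 2^(−t/h).

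- Minor bleed, E = 0: 79.4 to 87.1 mg/dL at 24 h and 63.0 to 75.8 at 48 h, against 80.
- Major bleed, E = 0: 119.1 to 130.6 mg/dL at 24 h and 94.5 to 113.7 at 48 h, against 130.
- Minor bleed, E = 45 mg/dL (assumed stable; eligibility allows historical activity below 50): 45 + 55 × 0.630 = 79.6 to 45 + 55 × 0.758 = 86.7 mg/dL at 48 h.

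With E = 0, staying at the limit needs h = 2 × ln 2 / ln(100/80) = 6.2 days for a minor bleed at 48 h, and h = 6 × ln 2 / ln(150/130) = 29 days for a major bleed at 6 days (counting Day 1 as the first observation day). So k may well be small, but single-infusion cases can arise through overshoot, slow elimination, residual endogenous fibrinogen or the investigator's decision. The documents do not fix k.

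**4. Direction of any bias, by two invented data sets.**

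- Three single-infusion successes, and three multi-infusion bleeds with one failure: FirstBLEED 5/6 = 83.3% (35.9 to 99.6); reading A gives 2/3 = 66.7% (9.4 to 99.2).
- One single-infusion failure after a switch to another concentrate, and five multi-infusion successes: FirstBLEED again 5/6 = 83.3%; reading A gives 5/5 = 100% (47.8 to 100). This presumes that the switch is not itself an excluding treatment error under SAP 6.2.

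The bias can go either way.

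**The case against.** The best defence is that the bullet refers to further infusions under the treatment schedule. If the schedule called for none, there is nothing to measure, and the 0% clause would cover only an infusion given or due without a dose calculation. This reading is sensible and may be what was intended. It does not dispose of the point, because the text does not state it and the clause as written says the opposite for a case with no calculated dose.

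A reader might infer that the rule removes the best responders and so biases the per-protocol success rate downward. The documents do not support that. Re-dosing follows the measured fibrinogen level together with the investigator's judgement of the child's condition (Protocol 3.2.2, 6.1.3.2), not cessation of bleeding alone. A single-infusion case may also be a failure: Protocol 4.4.1 and 4.8 allow a switch to another concentrate, and Protocol 9.3.1 generally scores such a case as none.

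It is also fair to say that the consequence is limited. The per-protocol analyses are secondary, everything is descriptive, and SAP 6.2 reviews exclusions before analysis, so an odd exclusion might be noticed. That lowers the risk but does not change the written rule. Finally, the half-life calculation argues against assuming that most bleeds need one infusion, which is why the full range of k is shown instead of one chosen value.

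**Conclusion.** The point holds as a defect of definition: the most direct reading of a stated criterion excludes treatment that the protocol itself foresees, in all three SAP sets. The damage is confined to the per-protocol analyses and to the SAP age subpopulations defined on BLEED-PP and SURG-PP. The primary FirstBLEED result does not change.

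The size depends on k, which is unknown. At the minimum of 6 first bleeds with all successes, the effect ranges from none (lower limit 54.1%, k = 0) to an empty set (k = 6). This rests on there being no other exclusions. It would go too far to say that the rule certainly empties the set, or that it shifts the success rate in a known direction. It should be corrected, because the criterion decides who is in a named analysis of the primary endpoint.

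**What to change.** In Protocol 9.2.6 and in the three per-protocol sets of SAP 6.1, add before database lock:

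*This criterion applies only if at least one further infusion was given or was due under the protocol; otherwise it is met. 0% is assumed only for a further infusion given or due for which no dose was calculated.*

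The word *due* needs a single meaning for this criterion. The level-based re-dosing rule (Protocol 5.4.3 and 6.1.3.2; for surgery 5.4.4 and 6.1.4.2) and the passages that leave the need for further infusions or the length of treatment to the investigator (Protocol 3.2.2, 3.2.3, the notes in 6.1.3.1 and 6.1.4.1, and 6.1.3.2) can give different answers for a child whose level falls below the limit after the investigator has judged one infusion enough. The sponsor should reconcile them; this review takes no position on which should govern.

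The cost is two sentences in each document plus that reconciliation. The definition change itself alters no treatment and needs no new assessments, since the plan already records each infusion and measures the level daily.
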